5.3 TREATMENT EXPOSURE

5.3.1 EXPOSURE

Since this is an open-label study, there is no blinding. The site pharmacist(s) or designee will be preparing study drug for infusion. Detailed study drug preparation and handling instructions will be provided to the investigational pharmacist in the Pharmacy Manual.

Total duration of exposure to study treatment during Induction period is defined as the number of days elapsed from date first dose to the date of Week 14 visit for patients who enter OLE, or otherwise, to the date of 4 weeks after last dose or the date of data cutoff for the primary analysis, whichever is earlier. The total duration of exposure to study treatment and total number of infusions received for the IP and OLE will be summarized using descriptive statistics for the Safety Analysis Set.

5.3.2 COMPLIANCE

The investigator is responsible for accountability of all study supplies, including study treatments, at the site and must maintain adequate records of all study treatment received and dispensed. These records will be used to evaluate protocol deviation with respect to treatment compliance.

The total number of infusions (PRA023) administered will be summarized using descriptive statistics during the IP for safety analysis set. Number of subjects with a missing dose during IP will be presented.

A complete infusion is defined as the infusion with at least 80% infusion volume (i.e., 200 mL) administered of the total volume (i.e., 250 mL). The total number of complete infusions administered will be summarized.

A by-subject listing of study drug administration and infusion interruption will be provided for the Induction Period and OLE period, sorted by subject ID number in ascending order.

5.4 PRIOR AND CONCOMITANT MEDICATION

Prior and concomitant medications will be classified into anatomical therapeutic chemical (ATC) drug classes using the World Health Organization (WHO) drug dictionary version March 2020 or newer.

A tabular summary showing the number and percentage of subjects taking CD agents (including corticosteroids) prior to the enrollment, and concomitant during the Induction period will be presented for all subjects in Safety Analysis Set. A similar table will be presented for OLE period for subjects in OLE analysis set.

Summary of prior and concomitant medications, separately for CD medications and non-CD medications, will include the number and percentage of subjects by ATC Classification level 2 and preferred term. A subject will be counted only once within a given drug class and within a given drug name, even if he/she received the same medication at different times. If any prior or concomitant medication is classified into multiple ATC classes, the medication will be summarized separately under each of these ATC classes. The summary tables will be sorted on decreasing frequency of drug class and decreasing frequency of drug name in a given drug class. In case of equal frequency regarding drug class (respectively drug name), alphabetical order will be used. In case any specific medication does not have ATC classification level 2 coded term, it will be summarized under “Unavailable ATC classification” category. Summaries will be based on the Safety Analysis Set. No formal statistical testing is planned.

Listings of prior and concomitant CD medications will be generated.

5.4.1 PRIOR MEDICATION

Prior medications are defined as the medication that started and stopped before the first dosing date. Only medications where the stop date is prior to the first dosing date will be considered prior. If the stop date is unknown or incomplete and the medications cannot definitely be considered as stopped prior to first dosing date then the medications will be considered as concomitant medications (e.g., partial stop date is May 2021, first dosing date is 15 May 2021, medication will be considered as concomitant).

5.4.2 CONCOMITANT MEDICATION

Any medication with a start date prior to or on the first dosing date and continuing to take after the first dosing date, or started after the first dosing date will be considered concomitant medications. In addition, concomitant medications with a start date after the last dosing date (concomitant medication taken during the safety follow-up period) will be presented in the follow-up medication

listing, as appropriate. If the start date of a medication is incomplete or missing, the medication will be assumed to be concomitant medication, unless the incomplete start date (month and/or year) or the stop date (complete or incomplete) clearly indicate that the medication started prior to first dosing date or later than 30 days after the last dosing date. Medication with completely missing start and stop dates will be included in the concomitant medication summary. Additionally, the use of prohibited medications will be summarized and listed.

5.5 MEDICAL AND SURGICAL HISTORY

Medical and surgical history will be coded using the most current available version of Medical Dictionary for Regulatory Activities (MedDRA version 24.0) and will include all relevant surgical and medical history including CD-related complications, other significant conditions or diseases relevant to the disease under study, previous surgeries for CD, and the extent and duration of disease at baseline.

A by-subject listing will be provided for those subjects with any medical/surgical history for the Safety Analysis Set.

5.6 PROTOCOL DEVIATIONS

Review of all protocol deviations will be performed on an ongoing basis during the conduct of the study. The number and percentage of subjects with major protocol deviations will be summarized. Subjects with important protocol deviations will be excluded from PP Analysis Set. The important protocol deviation could include, but are not limited to:

- Major protocol deviation related to certain study eligibility
 - Entry criteria that would impact on efficacy analyses: Inclusion criteria 2,3,or 4
- Major protocol deviation related to study treatment
 - Receiving incorrect investigated products, or
 - Missing ≥ 2 scheduled infusions during IP
- Unevaluable or missing Week 12 SES-CD score

A by-subject listing will be provided for those subjects with any protocol deviations before database lock. A separated by-subject listing will be provided for important protocol deviations that resulted in exclusion from the PP analysis set.

6 EFFICACY ANALYSES

Efficacy analyses for IP will primarily be based on the FAS, and supportive efficacy analysis will be based on PP, unless specified otherwise. Demographic data characteristics (height, weight, age, sex, race, and ethnic origin) will be listed by subject and summarized by CDx status and for the overall study population. Selected efficacy endpoints over time during the OLE will be summarized descriptively.

6.1 DERIVATION OF EFFICACY MEASUREMENTS

6.1.1 SIMPLE ENDOSCOPIC SCORE – CROHN’S DISEASE (SES-CD)

The SES-CD scores 4 endoscopic items (ulcer size, proportion of ulcerated surface, proportion of the surface area affected by any disease lesion, and stenosis) from 0 to 3, with higher scores

representing more severe endoscopic disease activity. Each variable is scored for the 5 intestinal segments (ileum, right colon, transverse colon, left colon, and rectum) and summed to provide the total variable score. The sum of each variable score ranges from 0 to 15, except for stenosis, where it ranges from 0 to 11, because 3 represents a stenosis through which a colonoscope cannot be passed and therefore, can only be observed once. Total SES-CD score is then calculated by summing the item scores (0-56 points). A score of zero is imputed for the missing items within a segment; if all components are missing, the total score will also be missing. [2] See Appendix A for additional details.

In general, a total SES-CD score can be calculated if the scores are available for at least 2 segments, and the total score is the sum of available segment scores, with the exception that if any segment is missing at Baseline, in which event the post-Baseline SES-CD will not include the specific segment.

Post-Baseline endoscopy performed out of study window can be used for the study visit (e.g., Week 12) if the procedure date is within the time window of 2 weeks prior to and 6 weeks after the date of study visit.

6.1.2 CROHN'S DISEASE ACTIVITY INDEX (CDAI)

The Crohn's Disease Activity Index(CDAI) consists of 8 items including physical examination items, extraintestinal manifestations, the hematocrit, and patient-reported outcome measures (number of liquid or very soft stools/day, abdominal pain, fever and general well-being), which are recorded by the subject in the electronic diary (or paper diary as backup in case of electronic diary not be available). A lookback to the 7 days prior to the clinic visit (Appendix B) will be used for CDAI score calculation. [3] Each item is multiplied by a weighting factor and summed to give

a total CDAI score, ranging from 0 to over 600 points, with higher scores representing more severe disease activity. Evaluable days do not include days of bowel prep, day of colonoscopy, and two days after colonoscopy.

If the full seven evaluable days of daily diary information for any of the patient-reported outcome measures (number of liquid stools, abdominal pain, general well-being) are not present, the following imputation rules will be applied:

1. If five or six days are available, the available data will be summed and reweighted for seven days. E.g. for five days: Abdominal Pain Score = $\text{SUM}(\text{five days}) \times 7/5$
2. If four or fewer days are available, then reach back to 10 days rather than 7 days prior to the visit. If there are at least 5 evaluable days of symptoms in the 10 day window, the available data will be summed and reweighted (if necessary) for the seven day score.
3. If there are still four or fewer evaluable days of symptoms in 10 days, then the component score will be considered missing.

The resulting days of eDiary used will apply to fever (a part of extraintestinal manifestation) and use of antidiarrheal medication.

For the component of extraintestinal manifestation, if the assessment is not done at a visit, data of evaluation from visits (including unscheduled visits) within 60 days prior to, or within 7 days after the study visit will be used. As fever is captured via eDiary, any presence of fever from the days of the eDiaries above will be counted as 1; 0 otherwise.

For the component of use of antidiarrheal medication, any recorded use of antidiarrheal medication from the days of eDiaries above will result in a 'Yes'; 'No' otherwise.

For the component of abdominal mass, if the assessment is not done at a visit, the last known status will be used.

For lab value of hemacrit, central lab value from the study visit should be used. If the study visit hemacrit is not evaluable, value from other visits within 60 days prior to, or within 7 days after the study visit will be used.

For body weight, if weight is not measured at the study visit, the last known weight prior to the study visit will be used.

CDAI score at a study visit will be considered missing if any of these components is missing according the rules above.

6.1.2.1 2-item Patient-reported Outcome Measure (PRO-2)

The PRO2 consists of two CDAI component items: daily stool frequency and abdominal pain. [4] Study participants record the number of liquid or very soft stools and rate abdominal pain (from 0-3) daily, excluding non-evaluable days. The average of the daily entries for the 7-day period is calculated and multiplied by a weighting factor to provide a total score for each component item. The total PRO2 score is then calculated by summing the component item scores. See Appendix C for additional details. The similar imputation rules (without reweighting) will be applied to the PRO-2 as in the CDAI.

6.1.3 PERIANAL DISEASE ACTIVITY INDEX (PDAI)

The Perianal Disease Activity Index (PDAI) will be used to evaluate severity of perianal disease. The PDAI incorporates 5 items: discharge, pain, restriction of sexual activity, type of perianal disease, and degree of induration. Each category is graded on a 5-point Likert scale ranging from no symptoms (score of 0) to severe symptoms (score of 4). Scores can range from 0 - 20, with higher scores indicating more severe perianal disease. See Appendix D for additional details.

6.1.4 GLOBAL HISTOLOGIC DISEASE ACTIVITY SCORE (GHAS)

The Global Histologic Disease Activity Score (GHAS) assesses the extent and/or severity of 7 histologic variables (Appendix E). [5] The total GHAS (range: 0-16) per segment is calculated by adding up the scores for each histological variable, with higher scores representing more severe disease activity. The overall total GHAS is the sum of all affected segments. Disease activity is scored separately for colonic (CGHAS) and ileal (IGHAS) biopsies.

6.1.5 ROBERTS HISTOPATHOLOGY INDEX (RHI)

The Roberts Histopathology Index (RHI) was developed by selecting items from the Geboes score that showed at least moderate intra-rater reliability and best predicted overall microscopic disease activity on a visual analogue scale. [6] The 4 items selected for inclusion include: 1) the extent of chronic inflammatory cell infiltration, 2) neutrophils in the lamina propria, 3) neutrophils in the epithelium, and 4) erosions and ulceration (see Appendix E). Each item is scored from 0 to 3 and multiplied by a weighting factor and summed to give the overall RHI score, with total scores ranging from 0 (no disease activity) to 33 (severe disease activity).

6.2 PRIMARY EFFICACY ENDPOINT

The primary efficacy endpoint, endoscopic improvement at Week 12, will be used to assess the efficacy of PRA023. The proportion of subjects in PP analysis set with endoscopic improvement at Week 12 will be tested against the null hypothesis of 12%, an upper bound of observed placebo rate from multiple CD trials (Table below and Table 6 of study protocol).

Clinical Trial	N	Placebo Endoscopic Response Rate (%)
Feagan et al. 2017	39	13
Vermeire et al. 2017	44	14
Sands et al. 2019	64	10.9
Selinger et al. 2018	59	3.4
Advance Study 2021	175	12
Motivate Study 2021	187	11
Average		10.7
Sample-size Weighted Average	568	9.5
95% CI		(7.1, 11.9)

6.2.1 PRIMARY ANALYSIS

The proportion of subjects with endoscopic improvement in PP analysis set will be estimated by the number of subjects who achieved the improvement at Week 12 divided by the total number of subjects in PP analysis set. The confidence interval for the proportion will be calculated using Wilson-score method (Wilson 1927). If the resulting lower bound of 95% CI is greater than 12%, the null hypothesis is, therefore, rejected at a 1-sided significance level of 0.025.

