--	--

	
drug level per therapeutic dose monitoring is greater than lower limit of detection.
 
31. Rituximab within 1 year prior to Day 1.
 
32. Parenteral corticosteroids within 4 weeks or rectal administration of corticosteroids within 2 weeks prior to Day 1.
 
33. Rectal administration of 5-ASA within 2 weeks prior to Day 1.
 
34. Tacrolimus, cyclosporine, mycophenolate mofetil (CellCept®), immunoadsorption columns (such as ProSORBA columns), D Penicillamine, Leflunomide, Thalidomide, chronic use of non-steroidal anti-inflammatory agents (NSAIDs), and aspirin > 81 mg/day within 2 weeks prior to Day 1.
 
35. Other investigational chemical agent within 30 days or other investigational biologic agent within 8 weeks or 5 half-lives (whichever is longer) of entry into the IP.
 
36. Prior exposure to PRA023.
 
Other Exclusion Criteria
 
37. Prisoners or subjects who are compulsorily detained (involuntarily incarcerated) for treatment of either a psychiatric or physical (e.g., infectious disease) illness.
 
38. Legal or mental incapacitation, or inability to understand and comply with the requirements of the study.
 
39. Known allergies, hypersensitivity, or intolerance to PRA023 or its excipients.

Statistical Methods:
	
Statistical methods will be detailed in the Statistical Analysis Plan (SAP). The SAP will provide details about methods of analysis and the specific planned analyses, and will be prepared and approved by Prometheus Biosciences and its designees before study database lock.
 
The analysis populations are defined as follows:
 

• Full analysis set (FAS): all subjects treated with Baseline SES-CD score

• Safety analysis set: all subjects treated

 
The following analyses will be performed:
 
Efficacy:
 
The primary efficacy endpoint, endoscopic improvement at Week 12, will be used to assess the efficacy of PRA023. The proportion of subjects in the per-protocol population with endoscopic improvement will be tested against the null hypothesis of endoscopic improvement rate of 12%, at a 1-sided significance level of 0.025. If significant, the 1st secondary endpoint of proportion of subjects in FAS achieving clinical remission will be tested against the null hypothesis of clinical remission rate of 16%, at a 1-sided significance level of 0.025.

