**Table 2 Schedule of Study Assessments – Induction Period**

Study Week	Study Visit							Early Termination	NOTES
	0	1	2	6	10	12			
	Study Day	1	8	15	43	71	85		
Visit window (days)	0	±1	±3	±3	±3	±3			
Procedure									
Eligibility Confirmation	X								
Randomization	X								Via IRT system
Complete Physical Examination						X	X		
Targeted Physical Examination	X		X	X	X				
Vital Signs	X	X	X	X	X	X	X		Heart rate, temperature, blood pressure; Take pre-dose (no more than 30 minutes pre-infusion), end of infusion, and end of observation period.
Weight	X	X	X	X	X	X	X		Needed for CDAI assessment
ECG	X					X	X		
Adverse Events Assessment	X	X	X	X	X	X	X		
Concomitant Medication	X	X	X	X	X	X	X		
Efficacy Assessments									
Ileocolonoscopy with Biopsy						X	X		Ileocolonoscopy to be performed within 10 days after Week 12 visit, or at early termination visit
Review eDiary Data from Subjects	X	X	X	X	X	X	X		Remind subjects to record in their eDiary daily
CDAI Assessment	X	X	X	X	X	X	X		
PDAI	X					X	X		
Fistula Drainage Assessment	X		X	X	X	X	X		
IBDQ	X			X		X	X		
Laboratory Testing									
CBC	X	X	X	X	X	X	X		
Chemistry Panel	X		X	X		X	X		
Fasting Lipid Panel	X					X	X		

	Study Visit							NOTES	
	Study Week	0	1	2	6	10	12		Early Termination
	Study Day	1	8	15	43	71	85		
Visit window (days)	0	±1	±3	±3	±3	±3			
Procedure									
Urinalysis	X		X	X		X	X		
Urine Pregnancy Test (WOCBP only)	X			X		X	X		
Pharmacokinetics	X a	X	X b	X b	X a	X	X	a. The PK sample at Week 0/Day 1 and Week 10 must be taken pre-dose, immediately following the end of infusion (within 30 minutes), and 1 hour after the end of infusion. b. The PK sample taken at Weeks 2 and 6 must be taken pre-dose (within 30 minutes prior to dosing).	
Immunogenicity	X a		X a	X a		X	X	a . To be taken pre-infusion	
Biomarkers									
Biomarkers	X		X	X	X	X	X	Serum at all visits; additional whole blood at Weeks 0, 6 and 12	
Soluble TL1A	X		X	X	X	X	X		
hsCRP	X	X	X	X	X	X	X		
Fecal Calprotectin	X			X		X	X		
Infusion	X		X	X	X			Include date, start and stop time, volume infused, and length of the IV infusion. Infusion observation period at Week 0/Day 1 and Week 2 will be 1 hour (2 hours for subjects in Czech Republic); 30 minutes for all subsequent infusions thereafter.	

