#### **9.2.2 Evaluation of Efficacy Parameters**

The primary efficacy endpoint, endoscopic improvement at Week 12, will be used to assess the efficacy of PRA023. The proportion of subjects in the per-protocol population with endoscopic improvement at Week 12 will be tested against the null hypothesis of 12%, an observed placebo

rate from multiple CD trials. Chi-square test will be used with a 1-sided significance level of 0.025. If significant, the 1st secondary endpoint of proportion of subjects in FAS achieving clinical remission will be tested against the null hypothesis of clinical remission rate of 16% (an observed remission rate for the placebo treated patients from multiple CD trials ([AbbVie 2021](#), [Feagan 2017](#), [Sands 2019](#), [Selinger 2018](#), [Vermeire 2017](#))).

The point estimates for the primary and secondary endpoints will be calculated along with 95% confidence interval for FAS and by CDx status (CDx+ or CDx-).

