10 CHANGES FROM PROTOCOL

Methods in this SAP different from the methods described in the protocol are summarized as follow:

- In Section 2, for objectives and endpoints that has accessing timepoint at Week 50, all timepoints at Week 50 were removed from this SAP. The final analysis of OLE data will be specified in a separate SAP.

- In Section 2 and Section 3.1, the definition for clinical response is refined so that responders will also include those patients who achieve clinical remission (CDAI < 150) but may not achieve ≥ 100 point reduction in CDAI from baseline.
- In section 2, additional exploratory endpoints (endoscopic remission, ulcer-free at Week 12, change in SES-CD segment score from baseline to week 12, clinical improvement by PRO-2 score, IBDQ remission or response,(steroid-free clinical remission for CDAI and by PRO-2, steroid-free clinical improvement by CDAI and by PRO-2, Clinical response by PRO-2 total score,) were add in the overall objectives and endpoints.
- In section 2, serum PD marker EHI was removed from the SAP. It will be analyzed when it becomes available.
- For analysis populations, PP analysis set was added.
- For evaluation of primary efficacy endpoint, the analysis specified in SAP V01 based on the method of multiple imputation was removed due to the known lack of sufficient correlation between SES-CD and CDAI scores in prior CD clinical trials. Instead, PP analysis set, which requires evaluable endoscopic score at Week 12, will be used and the confidence interval for the proportion will be calculated using Wilson-score method.
- Sensitivity analysis based on FAS was added to further access the robustness of primary analysis.
- For evaluation of secondary efficacy dichotomous or binary endpoint, the confidence interval for the proportion will be calculated using Wilson-score method, while non-responder imputation may apply for missing endpoint.
- For evaluation of the continuous secondary efficacy endpoint, PP analysis set and ANCOVA will be used for the change from baseline in SES-CD at Week 12. The median for the change from baseline in SES-CD score at Week 12 for PP analysis set will also be estimated and p-value for testing against no change will be reported using Wilcoxon rank test
- For evaluation of continuous exploratory efficacy endpoints, endpoints with multiple assessments over time, MMRM will be used. The 95% confidence interval for the LS mean for the change from baseline at Week 12 will be calculated.

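### The primary test runs on a per-protocol set that requires an evaluable Week 12 endoscopy, so subjects without one leave the denominator of a single-arm test against a fixed 12%

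*SAP*

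**What the plan says.** The primary endpoint is tested on a per-protocol population in both documents. Protocol 9.2.2: "The proportion of subjects in the per-protocol population with endoscopic improvement at Week 12 will be tested against the null hypothesis of 12" per cent. The protocol synopsis has the same rule. SAP 6.2.1 gives the estimator, "The proportion of subjects with endoscopic improvement in PP analysis set will be estimated by the number of subjects who achieved the improvement", taken over the PP total, and rejects if the Wilson 95% lower bound exceeds 12%.

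PP membership depends on what happens after dosing starts. SAP 5.6 lists "Unevaluable or missing Week 12 SES-CD score" among the deviations that lead to exclusion, together with two or more missed induction infusions, under the lead-in "The important protocol deviation could include, but are not limited to". SAP 10 confirms the requirement and explains that PP replaced multiple imputation: "Instead, PP analysis set, which requires evaluable endoscopic score at Week 12, will be used". Protocol 9.1 defines only the safety set and the FAS.

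An endoscopy is also scheduled for early leavers; Protocol Table 2 places it within 10 days after the "Week 12 visit, or at early termination visit". SAP 6.1.1 lets an out-of-window endoscopy stand for the visit "if the procedure date is within the time window of 2 weeks prior to and 6 weeks after the date of study visit". SAP 4.4, Table 2 gives Day 71 to 98 for the Week 12/ET ileocolonoscopy.

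The FAS (SAP 4.2.3) needs only treatment and baseline CDAI and SES-CD scores. SAP 6.2.2 plans a FAS analysis with a missing Week 12 SES-CD counted as non-response, as a sensitivity analysis. Clinical remission, the next test in the hierarchy (SAP 6.3.1 and 6.10), is tested in the FAS with missing counted as non-response.

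**The concern.** In a single-arm trial against a fixed number, the denominator matters as much as the numerator. If the subjects removed for lack of a Week 12 endoscopy are mainly treatment failures, the PP rate exceeds the rate among those treated, and nothing in the design corrects for it.

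The documents give some reason to expect this. Under Protocol 4.4.6, rescue medication is confined to the extension, and a subject who needs a new therapy for Crohn's disease should be withdrawn. An induction failure can therefore become an early termination. A subject who stops before about Day 71 leaves PP unless an endoscopy is done later, inside the window. One who stops late and is scoped in the window stays in, unless excluded for another reason.

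SAP Section 6 makes the FAS the default unless stated otherwise, so PP here is a declared exception and not a contradiction. The effect is still that the gatekeeping test uses a more lenient denominator than the clinical remission test it guards. The FAS analysis in 6.2.2 enters neither the rejection rule nor the gate, and nothing says what follows if it disagrees with PP. The further analysis in SAP 6.9, non-responder imputation within PP, adds little because PP already requires a Week 12 score. It could differ only if the discontinuation rule of 6.8.1 is meant to apply, which 6.9 does not say.

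**Working it through.** **Inputs.** N = 50, null rate 12%, assumed rate 27%, one-sided 0.025, power 80% (Protocol 8.2, SAP 3.2). Decision rule: Wilson 95% lower limit above 12% (SAP 6.2.1). The number excluded (m) and the response rate the excluded would have had (r) are my assumptions; neither document gives a dropout or missing-endoscopy rate.

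**1. The plan's own figure.** One-sample formula: n = [(1.96·√(0.12·0.88) + 0.842·√(0.27·0.73)) / 0.15]² = 45.4, or 51.8 with continuity correction. Power at 50 is 83.0% uncorrected and 78.7% corrected, so the stated 80% at N = 50 is reproduced approximately by the corrected version. Under the SAP's Wilson rule, 50 subjects need 11 responders (11/50, lower limit 12.75%). Exact power is P(X ≥ 11 | 50, 0.27) = 83.0% and exact type I error is P(X ≥ 11 | 50, 0.12) = 3.25%.

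**2. Pass mark by PP size.**

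| PP size | Excluded of 50 | Responders needed | Same count over 50 |
|---|---|---|---|
| 47–50 | 0–3 | 11 | 11/50 passes (12.75%) |
| 42–46 | 4–8 | 10 (10/46: 12.26%) | 10/50 fails (11.24%) |
| 38–41 | 9–12 | 9 (9/40: 12.32%) | 9/50 fails (9.77%) |

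**3. False-positive risk with the true all-treated rate fixed at 12%.** The expected number of responders among 50 is 6, so the PP rate is (6 − r·m)/(50 − m). PP error is the binomial tail at the pass mark for n = 50 − m. The FAS error, with missing as non-response, is P(X ≥ 11) from the same n and rate.

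| Excluded | Would-be response of excluded (r) | PP rate | PP error | FAS error |
|---|---|---|---|---|
| 5 (n = 45, need 10) | 0% | 13.33% | 6.9% | 3.1% |
| 5 | 6% | 12.67% | 5.2% | 2.2% |
| 5 | 12% (no bias) | 12.00% | 3.8% | 1.5% |
| 10 (n = 40, need 9) | 0% | 15.00% | 13.5% | 3.0% |
| 10 | 6% | 13.50% | 8.2% | 1.5% |
| 10 | 12% (no bias) | 12.00% | 4.4% | 0.6% |

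The no-bias rows show what the discreteness of the Wilson rule contributes. Exclusion bias itself adds up to 6.9 − 3.8 = 3.1 points with 5 excluded and 13.5 − 4.4 = 9.1 points with 10. With 0 to 3 excluded, all non-responders, the error is about 3.2% on either set.

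**4. Random number excluded.** If each of 50 subjects is a responder with probability 0.12, excluded and a non-responder with probability q, and otherwise an evaluable non-responder, PP error is 4.0%, 6.1% and 11.6% at q = 5%, 10% and 20%. The FAS error stays 3.25%.

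**5. Power under the two readings of 27%.** If 27% refers to evaluable subjects, FAS power is P(X ≥ 11 | n, 0.27): 83% at n = 50, 70% at n = 45 and 53% at n = 40. PP power at n = 45 and n = 40 is 81% and 79%. If 27% refers to all treated subjects, FAS power stays 83%.

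**The case against.** **The number of exclusions is unknown.** Nothing changes below 4 exclusions (8% of 50), and the 13.5% figure needs 10 exclusions, all non-responders, with a true rate of exactly 12%. SAP 10 notes weak correlation between SES-CD and CDAI, so a subject who leaves for symptoms need not be an endoscopic failure. This stands, and is why the sizes are conditional and the half-rate and no-bias rows are shown.

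**An early-termination endoscopy might count.** SAP 4.4 labels the row Week 12/ET and generally uses nominal visits, so an endoscopy before Day 71 could perhaps be analysed. The text is not fully clear, but the Day 71 to 98 range and the two-weeks-before limit in 6.1.1 both point to exclusion. The ambiguity affects the number excluded, not the principle.

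**The 12% has some margin.** It is presented as an upper bound on the placebo rate. The rows of Protocol Table 7 give a sample-size weighted mean of 10.9%. At that rate the PP error with all-non-responder exclusions is about 4.0% with 5 excluded (rate 5.44/45 = 12.1%) and 8.5% with 10 (5.44/40 = 13.6%). This softens the concern without removing it.

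**Non-responder imputation is not neutral.** If missingness is unrelated to response, the FAS test is conservative (1.5% and 0.6%), and power may fall. Nor do the documents say how the historical trials counted missing endoscopies. Both points stand as costs to be weighed.

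**The plan is open about its choice.** PP is prespecified, exclusions are listed, the FAS analysis will be reported, and this is an open-label proof-of-concept study. Disagreement would be visible, but PP would still decide success and open the gate. The reason given in SAP 10 argues against multiple imputation; non-responder imputation does not depend on that correlation.

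**Conclusion.** The concern holds. The primary decision rests on a set defined by a post-baseline event, in a design with no comparator, while the analysis that keeps every FAS subject is planned but decides nothing. From 4 exclusions upward the same responder count can succeed on PP and fail on the FAS. At a true all-treated rate of 12%, the false-positive risk on PP is 5.2% to 6.9% with 5 excluded and 8.2% to 13.5% with 10, if the excluded would respond at between half the null rate and not at all. The SAP claims 2.5%. The definition of the sets is clear from the text; the size depends on how many subjects lack an in-window endoscopy and how they would have responded, which the documents do not give.

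**What to change.** In SAP 6.2 and 6.2.1, Protocol 9.2.2 and the synopsis, make the FAS analysis of SAP 6.2.2 (missing Week 12 SES-CD counted as non-response, Wilson interval against 12%) the deciding analysis and the gate to clinical remission. Make PP supportive. Reword SAP 6.9 to say what non-responder imputation changes within PP, or delete it. State in SAP 3.2 whether 27% refers to all treated or to evaluable subjects.

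The analysis is already planned, so the direct cost is wording. The price is a lower point estimate when endoscopies are missing and, if 27% was meant for evaluable subjects, the power loss shown above. In that case N = 50 needs a new justification: with 10% missing the all-treated rate becomes 0.9 × 27% = 24.3%, and 80% power by the same formula needs about 66 subjects (74 with continuity correction).
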